## 1. Protocol Synopsis

PROTOCOL TITLE:	A Phase III study of efficacy, safety and tolerability of Chronocort® compared with standard glucocorticoid replacement therapy in the treatment of congenital adrenal hyperplasia (CAH)
PROTOCOL No:	DIUR-005
PRINCIPAL COORDINATING INVESTIGATOR	██████████ ██████████ ██████████████████ ██████████████████ ██████
SPONSOR:	Diurnal Limited [name] UK
INVESTIGATIONAL PRODUCT:	Chronocort® (Hydrocortisone Modified Release Capsule)
PHASE OF DEVELOPMENT:	Phase III
STUDY DESIGN	Parallel arm, randomised, open study
INCLUSION CRITERIA	

 
Known CAH due to 21-hydroxylase deficiency (classic CAH) diagnosed in childhood with documented (at any time) elevated 17-hydroxyprogesterone (17-OHP) and/or androstenedione (A4) and currently treated with hydrocortisone, prednisone, prednisolone or dexamethasone (or a combination of the aforementioned glucocorticoids) on a stable glucocorticoid therapy for a minimum of 6 months.
 
Male or female subjects aged 18 and above.
 
Provision of signed written informed consent.
 
Non-pregnant, non-lactating females who are post menopausal, naturally or surgically sterile, or of childbearing potential with a negative urinary pregnancy test and using a medically acceptable method of contraception (Note: females presenting with oligomenorrhoea or amenorrhoea who are aged ≤55 years of age should be considered potentially fertile and therefore, as well as undergoing pregnancy testing like all other female subjects, will be expected to be using an acceptable method of contraception).
 
Plasma renin activity (PRA) less than 1.5 times the upper limit of normal (ULN) at screening or within 3 months prior to screening, except in subjects who have been diagnosed with hypertension where the renin is not being used to monitor fludrocortisone replacement.
 
	
EXCLUSION CRITERIA	

 
Co-morbid condition requiring daily administration of a medication (or consumption of any material) that interferes with the metabolism of glucocorticoids.
 
Clinical or biochemical evidence of hepatic or renal disease. Creatinine over twice the ULN or elevated liver function tests (ALT or AST >2 times the ULN).
 
Subjects on regular daily inhaled, topical, nasal or oral steroids for any indication other than CAH.
 
Subjects with any other significant medical or psychiatric conditions that in the opinion of the investigator would preclude participation in the trial.
 
History of malignancy (other than basal cell carcinoma successfully treated >6 months prior to entry into the study).
 
Participation in another clinical trial of an investigational or licensed drug or device within the 3 months prior to inclusion in this study.
 
Subjects with a history of bilateral adrenalectomy.
 
Subjects having previously been exposed to Chronocort®.
 
Subjects who routinely work night shifts and so do not sleep during the usual nighttime hours.
 
Subjects unable to comply with the requirements of the protocol.
 
	
STUDY DURATION:	
After screening and baseline evaluation, subjects will either be randomised to Chronocort® or continue their standard therapy. Treatment will continue for 6 months, during which times the glucocorticoid dose in both treatment groups will be titrated according to an agreed algorithm to optimise control of the disease. After	

completion of the 6-month study period, all subjects may then enter a period of open-label treatment with Chronocort® as part of an open-label extension study (to be conducted under a separate protocol).	
NUMBER OF SUBJECTS: A sample size of 102 subjects provides greater than 95% power and 2-sided alpha 5% to demonstrate a fall in the logarithm of the mean daily unsigned standard deviation score of 17-OHP relative to the standard glucocorticoid replacement therapy group. It is assumed that (i) the mean fall in the Chronocort® group will be the same (0.78) as that observed in the phase II study (DIUR-003) (ii) the mean fall in the standard therapy group will be 0.2 (approximately 25% of the Chronocort® phase II study fall) and (iii) the standard deviation of the fall (0.681) is that seen in the phase II study. The study is powered to ensure that there can be a reasonable description of the comparison of Chronocort® with a variety of standard therapies. 120 subjects will be randomised to this study which will account for an inevaluability rate of 15%. Individual sites should not recruit more than 25 subjects without first consulting the sponsor.	
TEST PRODUCT, DOSE AND MODE OF ADMINISTRATION:	Chronocort® will be provided as 5mg, 10mg and 20mg capsules for oral administration. The starting dose for each subject will be based on the subject's previous glucocorticoid therapy dose and then dose titrated to effect. The morning dose of Chronocort® (approximately 1/3 rd of the total daily dose) should be taken at 07:00 hours on an empty stomach at least 1 hour before a meal and the evening dose (approximately 2/3 rd of the total daily dose) should be taken at 23:00 hours at least 2 hours after the last meal of the day.
REFERENCE THERAPY, DOSE AND MODE OF ADMINISTRATION:	Continuing previous oral glucocorticoid therapy titrated to effect.
OBJECTIVES: Primary Objectives: To demonstrate the superior efficacy of Chronocort® compared with standard glucocorticoid replacement therapy in the treatment of CAH based on 17-OHP. Secondary Objectives: In adult subjects with CAH: 
 
• To assess the safety and tolerability of Chronocort® treatment in adult subjects with CAH over a 6-month period.
 
• To assess the efficacy of Chronocort® with regard to the effect on A4 over the 6-month treatment period.
 
• To assess the impact of Chronocort® on body composition (using dual energy X-ray absorbtimetry [DEXA]) – fat mass, lean mass and total bone density – at selected sites.
 
 Exploratory Objectives: 
 
• To assess the efficacy of Chronocort® with regard to the effect on testosterone levels over the 6-month treatment period.
 
• To assess the impact of Chronocort® on cardiovascular (CV) risk (evaluated using high-sensitivity C-reactive protein [hsCRP]).
 
• To assess the impact of Chronocort® on bone markers of serum C-terminal cross-linked telopeptide (CTX) and osteocalcin (after fasting).
 
• To assess changes from baseline in glucose and insulin in the morning (after fasting)
 
• To assess changes from baseline in glycated haemoglobin (HbA1c) and PRA in the morning.
 
• To assess the impact of Chronocort® on quality of life (QoL) using SF-36®, Multidimensional Assessment of Fatigue (MAF), and EQ-5D™.
 
• To assess subject compliance in subjects treated with Chronocort® over a 6-month period.
 
	
ENDPOINTS: Primary Endpoint: The primary efficacy endpoint is the change from baseline to 24 weeks of the mean of the 24-hour standard deviation score (SDS) profile for 17-OHP. The SDS profile is calculated as the SDS of log-transformed 17-OHP concentration unsigned.	

*Secondary Endpoints:*

1. The change from baseline to 24 weeks of the mean of the 24-hour SDS profile for A4 (calculated in the same way as the primary endpoint).
2. The presentation of 17-OHP and A4 by individual baseline treatment strata in the study will be presented in the same manner as the primary endpoint (using 24-hour SDS profile at 24 weeks).
3. 17-OHP and A4 levels at 09:00 as a responder analysis (i.e. the number of subjects achieving results in the optimal range).
4. Changes relative to standard glucocorticoid replacement therapy in body composition (DEXA) (fat mass, lean mass and total bone density) to be measured at all sites except Germany.

*Exploratory Endpoints:*

1. Partial area under the curve (AUC) of 17-OHP at 15:00-23:00, 23:00-07:00, and 07:00-15:00 (all refer to actual clock time of sampling).
2. The primary endpoint measure will also be presented for the profiles measured at 4 and 12 weeks for the purposes of titration.
3. Changes relative to standard treatment in the following:
  - a. Bone markers – serum CTX and osteocalcin (after fasting)
  - b. hsCRP
  - c. Assessment of glucose and insulin in the morning (after fasting)
  - d. Assessment of HbA1c, total testosterone, and PRA in the morning
  - e. QoL using SF-36®, MAF, and EQ-5D™
4. Use of glucocorticoids at beginning and end of the study will be presented both as individual glucocorticoids used, and as calculated hydrocortisone equivalents using accepted conversion constants for the calculations.

*Safety Endpoints:*

1. Routine haematology, biochemistry, physical examination, vital signs, urinalysis, electrocardiogram (ECG).
2. Clinical adverse events (AEs) – particular note of use of sick day rules and Addisonian crises. Under or over-replacement with glucocorticoids will be considered in the efficacy endpoints.
3. Changes relative to the standard treatment in weight, body mass index (BMI), waist circumference, and blood pressure (BP).

**METHODOLOGY:**

As part of the baseline assessment, subjects will be admitted overnight for a 24-hour endocrine profile whilst on their standard therapy. Subjects will attend the study site in the morning and have a profile taken: 17-OHP and A4 at 15:00, 17:00, 19:00, 21:00, 23:00, 01:00, 03:00, 05:00, 07:00, 09:00, 11:00, 13:00 and 15:00.

Baseline bloods will be taken on the second morning and will include: safety measurements, all secondary endpoints to be measured – PRA, fasting osteocalcin and CTX, DEXA scan for body composition (except Germany) (DEXA scan may be performed at other times up to 2 weeks before baseline if scheduling proves difficult), insulin and glucose, HbA1c, QoL, height, weight (BMI to be calculated) and waist circumference. After these measurements have been taken, the subject will be randomised to Chronocort® or to continue on their standard care. Randomisation will be stratified by baseline treatment:

1. hydrocortisone only or
2. prednisone or prednisolone, alone or in combination with hydrocortisone
3. dexamethasone only or in combination with any other glucocorticoid

The initial dose setting at the start of the Chronocort® treatment will be based on hydrocortisone dose equivalent of baseline therapy in accordance with standard clinical practice. Further dose refinement/titration will be conducted in both treatment groups as necessary after 4 weeks and 12 weeks using a standardised titration algorithm after the subject has been re-admitted for further 24-hour profiles, to include 17-OHP and A4. Safety endpoints and PRA will also be measured at the 07:00 morning sample at each profile.

At 6 months, all the baseline tests will be repeated (including the 24-hour profile). All subjects may then continue on Chronocort®, whatever their randomised treatment, as part of an open-label extension study (to be conducted under a separate protocol).

**Blinding:** The decision to change doses in both treatment groups will be made by an independent blinded physician but the actual change in dose will be made by the local investigator looking after the subject. The intention of dose adjustment is to optimise control of CAH according to current standard of care based on subject symptoms and the measurement of androgens, as is currently recommended to clinical practice.

Stress doses of hydrocortisone will be given for intercurrent illnesses as medically indicated according to “sick day rules”. Fludrocortisone dose adjustment will be allowed if medically indicated and will be based on

BP measurements and laboratory data (goal supine PRA above the lower limit and <1.5 times ULN).

- Dose changes in both treatment groups will be under the direction of an independent blinded physician and will be made following an inpatient assessment of symptoms and androgen levels.
- Dose adjustment will be based on clinical symptoms using the “signs and symptoms of adrenal insufficiency questionnaire” and the measurement of the 17-OHP and A4 profiles.
- The 5 samples taken between 01:00 and 09:00 will reflect the glucocorticoid dose taken in the evening or last thing at night on standard or Chronocort® therapy and the 5 samples taken between 11:00 and 19:00 will reflect the morning glucocorticoid dose on standard or Chronocort® therapy. Dose adjustments will be considered if 3 or more of the 5 sample times show out of range values for 17-OHP or A4.

For subjects continuing on standard therapy the local investigator can change the daytime and evening doses of the standard therapy (within the limits set by the independent blinded physician) but the timing and the drugs used must not be changed. Dose adjustment will use the lowest dose adjustment available with the specific therapy, so generally for hydrocortisone this will be 5mg, for prednisolone 1mg and dexamethasone 0.25mg.

Where 17-OHP and A4 show inconsistent trends the A4 parameter will take precedence in directing dose adjustment.

If required, dose adjustments will be made within 2 weeks of the week 4 and week 12 visits when biochemical results are reviewed.

- All subjects (whether or not there has been a titration) will receive a telephone call one week after any dose adjustments to enquire as to whether there have been any AEs, and reinforce any other protocol requirements.
- No dose adjustments outside of the protocol-defined dose adjustments should be conducted, unless clinical signs and symptoms indicate an immediate need. In such cases the Sponsor’s medical monitor must be contacted (preferably before any dose changes are implemented). Any such unscheduled dose adjustments should be based on clinical symptoms only, with repeated androgen testing discouraged and must be pre-approved by the Sponsor’s medical monitor. The rationale for any dose adjustment, by both the independent blinded physician and also any changes made by the local investigator, will be recorded in the electronic case report form (eCRF).
- In subjects who have undetectable androgens at baseline on their regular medication, caution will be taken over dose reduction so as to avoid the risk of suppressed pituitary-adrenal axis occurring in these subjects.

#### **STATISTICAL METHODS:**

The Statistical Analysis Plan (SAP) must be finalised before any subject is randomised into the trial.

Efficacy: The primary efficacy endpoint is the change from baseline to 24 weeks in the primary efficacy variable (natural logarithm of the mean over the 24-hour SDS profile for 17-OHP). The primary efficacy endpoint will be compared between treatment groups within a Normal linear analysis of covariance (ANCOVA) model with baseline treatment category and baseline SDS as covariates. Exploratory analyses will investigate the sensitivity of the results to the transformation of the endpoint and to the form of the model. Secondary endpoints will also be analysed as a change from pre-randomisation baseline to end-of-study. To ensure that the treatment effect of Chronocort® is not all as a result of non-hydrocortisone based regimes being different in achieving control, the effect of Chronocort® within baseline treatment subgroups will be presented.

Safety: Summary vital signs change from baseline data will be presented in tabular form, by dose level across time, with N, mean, standard deviation (SD), median, quartiles, minimum and maximum as appropriate.

Summary ECG (heart rate, PR interval, QRS width, QT interval and QTC interval) change from baseline data will be presented in tabular form, by dose level across time, with N, n, mean, SD, median, minimum and maximum as appropriate.

AEs will be coded using the latest version of the MedDRA drug dictionary. Data will be summarised using preferred term and primary system organ class. Only treatment-emergent AEs, being events with an onset at or after the first administration of study drug, will be presented in summary tables. Where changes in severity are recorded in the eCRF, the most severe incidence of the AE will be reported in the tables. Rates will be calculated as the proportion of subjects with at least one AE related to the number of subjects treated in each treatment group. Frequency tables will be provided concerning severity and drug relationship.

Absolute and change from baseline laboratory variables (haematology, biochemistry) will be summarised by treatment group (N, n, mean, SD, median, quartiles, minimum and maximum) at each time point. Shift tables from pre-dose to each time point for laboratory variables (haematology, biochemistry) will be presented. The 3 x 3 cross tabulations (from low, normal and high to low, normal and high) will be presented by treatment group. Urinalysis variables will be listed by subject and time point. Values outside the normal ranges (provided with the laboratory report) will be flagged in the subject data listings.

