### 13.7 Safety Analysis

Safety variables, will be listed and summarised by treatment, stratum and timepoint.

The nature, severity, relatedness, duration, outcome and seriousness and outcome of all AEs will be listed. The subject incidence of treatment emergent AEs will be tabulated by system organ class, preferred term, severity and relatedness. Tables will be provided of AEs of special interest, SAEs, SUSARs, AEs leading to withdrawal and fatal AEs.

Shift tables will be presented for laboratory variables and vital signs. Abnormal findings on physical examination and from ECG will be tabulated. Listings of laboratory data, vital signs, physical examination and ECG will have abnormal findings marked, together with an indication of whether or not that finding was clinically significant.

The versions of the following international dictionaries current at the time of study conduct will be used for medical coding:

- Diagnoses: MedDRA
- Medications: WHO Drug Dictionary including ATC classification
- Adverse events: MedDRA

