## 7. Treatment comparisons

### 7.1. General

The comparison in all analyses will be between the Chronocort® treatment group and standard glucocorticoid replacement therapy.

For the stratified secondary and exploratory analyses and the stratified analysis of the primary endpoint, comparisons will be presented for subgroups defined by the pre-baseline standard treatment.

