## 11.6. Electrocardiogram (ECG)

The following ECG data will be collected: heart rate, PR interval, QRS width, QT interval and Bazett's and Fridericia QTc interval (QTcB and QTcF).

The change from baseline will be calculated and summary statistics will be tabulated for both absolute values and change from baseline by treatment group, visit and dose level. Abnormal findings will be tabulated by visit showing a frequency count and percentage of subjects with at least one abnormal finding.

ECG results will be listed and abnormal findings will be marked, together with an indication of whether or not that finding was clinically significant. Values with a change from baseline > 30 msec in QT interval, QTcB and QTcF will be flagged in the listing.

The following reference ranges will be used to determine the categories for the ECG shift table, and to mark the abnormal (high/low) findings in the ECG listing:

- Heart rate: Low < 40 msec; Normal  $\geq$  40 msec to  $\leq$  110 msec; High > 110 msec
- PR interval: Low < 120 msec; Normal  $\geq$  120 msec to  $\leq$  220 msec; High > 220 msec
- QRS width: Low < 70 msec; Normal  $\geq$  70 msec to  $\leq$  120 msec; High > 120 msec
- QT interval: Low < 330 msec; Normal  $\geq$  330 msec to  $\leq$  450 msec; High > 450 msec
- QTcB: Low < 350 msec; Normal  $\geq$  350 msec to  $\leq$  450 msec; High > 450 msec
- QTcF: Low < 350 msec; Normal  $\geq$  350 msec to  $\leq$  450 msec; High > 450 msec

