## 12. Changes from the planned analyses

At the time of finalising the SAP version 2.0, there are minor changes from the planned analyses specified in the protocol. For routine clinical laboratory variables (haematology and clinical biochemistry) shift tables to each visit relative to baseline have been replaced with shift tables to minimum on-treatment versus baseline and to maximum on-treatment versus baseline. This is judged to be a more conservative approach to detecting potential safety signals from clinical laboratory data. For vital signs, the split by dose level has been removed from the summaries of absolute values and change from baseline over time, due to the low number of subjects per category. Instead this will be assessed via listings. For a similar reason, the split by dose level has been removed from the summary of abnormal ECG results.

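### SAP 11.6 keeps a dose-level split for the numeric ECG summaries that SAP 12 dropped elsewhere for small cells, and states no all-doses summary per arm

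*Protocol*

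**What the plan says.** Four places govern how ECG values are tabulated.

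- Protocol synopsis, Statistical Methods (Safety): "QT interval and QTC interval) change from baseline data will be presented in tabular form, by dose level across time". The sentence does not name treatment group.
- Protocol 13.7: "Safety variables, will be listed and summarised by treatment, stratum and timepoint". Section 13.3.5 counts ECG among the safety variables.
- SAP 11.6: summary statistics for "absolute values and change from baseline by treatment group, visit and dose level". On abnormal results it says: "Abnormal findings will be tabulated by visit showing a frequency count and percentage of subjects with at least one abnormal finding".
- SAP 12: "For vital signs, the split by dose level has been removed from the summaries of absolute values and change from baseline over time", the reason being "due to the low number of subjects per category". For a similar reason, "the split by dose level has been removed from the summary of abnormal ECG results". The numeric ECG summaries are not mentioned.

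SAP 11.6 also sets reference ranges for an ECG shift table. The table list in SAP 14.1 has no such table. It has two numeric ECG tables, one over time and one for change from baseline, and neither title mentions dose.

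**The concern.** The numeric ECG summaries use the same safety population and the same doses as the vital signs. If dose cells are too small for a mean change in blood pressure, they are too small for a mean change in QTcF or PR interval. The SAP acted on that reason for vital signs and for abnormal ECG results, but not for ECG intervals. This looks like an incomplete edit.

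Sparse cells are not the only problem. Doses in both arms are reviewed after the week 4 and week 12 profiles and may be changed on hormone levels and symptoms. At weeks 12 and 24, a subject's dose level is therefore partly an outcome, and arms set side by side within a level are no longer the groups that were randomised. The documents also do not define dose level for a comparator arm that uses hydrocortisone, prednisone, prednisolone, dexamethasone and combinations.

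ECG is a named safety endpoint. What is at stake is whether the report shows a plain mean change per arm and visit for each ECG parameter, or only a grid of small cells that the reader must add up.

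**Working it through.** **Texts side by side: factors named for the numeric summaries**

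| Source | Factors |
|---|---|
| SAP 11.4.2 haematology, 11.4.3 biochemistry, 11.4.4 continuous urinalysis, 11.5 vital signs | treatment group, pre-baseline therapy, visit |
| Protocol 13.7, all safety variables | treatment, stratum, timepoint |
| Protocol synopsis, ECG | dose level, time |
| SAP 11.6, ECG | treatment group, visit, dose level |

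Among these safety domains, ECG is the only one in the SAP still split by dose and the only one not split by pre-baseline therapy. SAP 11.6 therefore departs from protocol 13.7 in two ways: it adds dose and omits stratum.

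**What a dose level could be.** Protocol section 8 (Dose Adjustment) gives the usual adjustment steps as 5 mg hydrocortisone, 1 mg prednisolone and 0.25 mg dexamethasone. With the SAP 9.2.3 factors, these in hydrocortisone equivalents are 5 × 1 = 5 mg, 1 × 5 = 5 mg and 0.25 × 80 = 20 mg. SAP 11.6 does not say whether levels are on the drug's own scale or in equivalents, nor whether they are single doses or bands. The Chronocort starting dose is capped at 30 mg and no such cap is stated for the standard arm, so the two dose distributions need not overlap fully.

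**Size of the arms.** The ECG plan states no figure of its own. The nearest design figure is the number randomised: 102 / (1 − 0.15) = 120, as the sample size section says. With 1:1 allocation (assumed, since I find no ratio stated), that is 60 per arm.

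**Cost of splitting.** Spread 60 per arm evenly over K levels, so n = 60/K per arm per cell at a visit. The 95% half-width for a difference of two cell means, in units of the between-subject SD, is t(0.975, 2n − 2) × √(2/n).

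| K | n per arm per cell | t × √(2/n) | Half-width (SD) | Ratio to unsplit |
|---|---|---|---|---|
| 1 | 60 | 1.980 × 0.183 | 0.36 | 1 |
| 4 | 15 | 2.048 × 0.365 | 0.75 | 2.1 |
| 6 | 10 | 2.101 × 0.447 | 0.94 | 2.6 |
| 8 | 7.5 | 2.160 × 0.516 | 1.12 | 3.1 |
| 10 | 6 | 2.228 × 0.577 | 1.29 | 3.6 |

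I leave the result in SD units because the documents give no SD for a change in QTc. K is an assumption. An uneven spread would make some cells larger and others smaller than shown.

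**Timing.** The week 4 ECG is taken at Visit 2, before the first titration, so apart from unscheduled changes dose there still reflects the starting dose. Selection by response applies at weeks 12 and 24.

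**The case against.** A reader might infer that no between-arm ECG comparison is planned, or that an ECG difference between arms could be neither seen nor excluded. The documents do not support that.

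- SAP 11.6 names treatment group and visit as table factors. Only the synopsis sentence leaves the arm out.
- Protocol 13.7 requires a summary by treatment, and SAP 7.1 says: "The comparison in all analyses will be between the Chronocort® treatment group and standard glucocorticoid replacement therapy".
- The two numeric ECG tables in SAP 14.1 carry no dose split in their titles, so the programmed tables may turn out to be pooled.
- The abnormal-findings table has no dose split. ECGs are listed by subject, with abnormal and clinically significant results marked and changes above 30 msec in QT, QTcB and QTcF flagged.
- Cells that show N and mean can be recombined exactly into arm means.

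The half-widths also need care. The plan specifies no test or confidence interval for ECG, so they illustrate sparseness and do not describe a planned inference. They should not be set against the 30 msec flag, which is a threshold for one subject's change and not a margin for a difference in means. The objection that dose level might mean a few broad bands, or hydrocortisone equivalents, is fair too, because the SAP does not say.

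All of this limits the consequence. It does not explain why a split judged too thin for vital signs and abnormal ECG results stays for ECG intervals, or why SAP 11.6 and protocol 13.7 name different factors. Following the synopsis is no explanation either: the synopsis asks for the same split for vital signs, and SAP 12 removed it there.

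**Conclusion.** The inconsistency is real and its consequence is modest. SAP 11.6 specifies arm by visit by dose level for ECG values and changes, states no all-doses summary per arm, and conflicts with protocol 13.7 and with the reasoning in SAP 12. Read literally, it yields cells of about 15 down to 6 subjects per arm against about 60 unsplit. From week 12 those cells are also shaped by titration. The cell sizes assume 1:1 allocation, everyone contributing at the visit, an even spread, and 4 to 10 levels.

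The effect is confined to descriptive safety tables. No data are lost, and a pooled summary can be produced from what is collected. Two smaller gaps go with it: the abnormal-findings sentence does not name treatment group, and the ECG shift table mentioned in 11.6 is missing from list 14.1.

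**What to change.** - **SAP 11.6, numeric summaries.** Tabulate absolute values and changes by treatment group, pre-baseline therapy and visit, pooled over dose. Require the column for the whole arm, which SAP 7.2 treats as optional. Three even strata would hold 20 subjects per arm each (half-width 0.64 SD by the same formula), so the arm total is what gives the comparison on about 60 per arm. Show dose in the ECG listing.
- **SAP 12.** Log the removal of the dose split for numeric ECG summaries with the reason already given for vital signs. Protocol section 13 lets minor statistical changes be documented in the SAP and study report, so the synopsis needs no amendment.
- **SAP 11.6, abnormal findings.** State that the table is by treatment group and visit.
- **SAP 11.6 and 14.1, shift table.** Either add the ECG shift table to the list or delete the reference to it.

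The cost is a few sentences of SAP text and simpler table shells. The dose breakdown remains available in the listings, as SAP 12 already arranges for vital signs.
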